4.1 Sample size

4.1.1 Sample size calculation (pre covid)

For the primary outcome ("Healthy baby"), in order to detect a difference in babies born "healthy" of 8% between the control and intervention arm, with 90% power and a 5% significance level, we would require at least 866 women per arm (i.e. 1732 total). This calculation also assumed an outcome proportion of 69% in the control arm, accounts for clustering within the intervention arm with an intra-cluster correlation (ICC) of 0.05 (in the intervention arm), mean group sizes of 8 with cluster size variability assuming Poisson distribution and assumes 10% drop-out in both arms. This sample size provides 84.8% power to detect a difference between arms of 7.3% in our, former primary outcome, spontaneous vaginal birth. Thus, a sample size 1732 is sufficiently powered to detect changes in both the primary outcome and SVD (now a secondary outcome).

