4.1.2 Sample size calculation (recruitment unpaused)

With the approval of the TSC an extension to allow the recruitment of another n=566 women to the study in addition to the sample size above has been made after the trial was paused. This results in a final total sample size targe of n=2190. The reasons for proposing this sample size are described in the following.

The trial has been paused to recruitment because of the Covid-19 pandemic. In person pregnancy circles were stopped and women were returned to one-to-one care. At this point:

- 794 women were recruited prior to the pandemic.
- 532 women recruited prior to the onset of the pandemic had not quite completed the intervention period but had the chance to receive a high or moderate dose of the intervention.
- 176 women recruited prior to the onset of the pandemic only had the opportunity to receive a low/very low dose of the intervention.
- Finally, another 122 women were recruited and had their pregnancy during a period when no intervention delivery was possible.

At this moment, the recruitment of 106 additional women would have been needed to reach the pre-specified sample size of 1732. But since some women only received low/very low or no dose of the intervention, we revised the sample size calculation to address the reduced chance of observing the pre-hypothesised effect size in the cohort already recruited.

With the approval of the TSC the decision was made to exclude all women who during the pandemic were not able to receive the intervention or were only able to receive a low/ very low dose during the pandemic from the primary outcome analysis (NB data from these women will still be analysed, just not as part of the primary outcome analysis). Additional women are recruited to replace these n=298 women. For the participant cohort who could have received a moderate or high dose of the intervention during the pandemic the assumption was made the treatment effect was halved which

requires an inflation of the sample size by n=160 to maintain pre-specified power. Thus together with 108 participants who had yet to be recruited the total post-pandemic recruitment target is n=108+160+298=566.

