5.5 General analysis principles

The analysis of primary, secondary, and, where possible, additional outcomes will be adjusted for the stratification factors which were used during randomisation, centre, and ability to speak English, only. All main analyses will be performed on a complete case basis (ignoring missing data) for the outcomes in question. A missing category will be created for the only covariate in the models "ability to speak English". The significance for statistical tests (alpha) will be 5%, all confidence intervals will be presented at the 95% level and all p-values will be two-sided. As the intervention arm includes group pregnancy circles, clustering will be accounted for in the intervention arm using pregnancy

circles as the units of clustering, while participants in the control arm will be modelled as a cluster size of one [1].

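### The 84.8% power for spontaneous vaginal delivery belongs to the pre-pandemic cohort and is never restated; with the plan's halved effect carried over, the final design gives about 76%, or 70–78% in all 2190 women

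*SAP*

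**What the plan says.** SAP 4.1.1, headed as the pre-covid calculation, sets the trial at "at least 866 women per arm (i.e. 1732 total") for an 8-point difference in the healthy baby composite, "with 90% power and a 5% significance level". For SVD it adds: "This sample size provides 84.8% power to detect a difference between arms of 7.3% in our, former primary outcome, spontaneous vaginal birth". It concludes: "Thus, a sample size 1732 is sufficiently powered to detect changes in both the primary outcome and SVD (now a secondary outcome").

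SAP 4.1.2, headed as the calculation after recruitment was unpaused, revises the cohort. It counts 794 women recruited before the pandemic, 532 who could receive a moderate or high dose, 176 who could receive a low or very low dose, and 122 who could receive none. The last two groups (298 women) leave the primary outcome analysis and are replaced. In the 532 the treatment effect is assumed halved, which the SAP says "requires an inflation of the sample size by n=160 to maintain pre-specified power". With 108 women still to recruit, the added recruitment is 566 and the total 2190. Of the 298 women it says: "NB data from these women will still be analysed, just not as part of the primary outcome analysis".

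No SVD power is given for this revised design, and no SVD control rate is given anywhere in the SAP.

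**The concern.** SVD is the only secondary outcome for which the SAP states a power and draws a conclusion from it. It was the primary outcome at the grant stage and is listed first among the secondary outcomes in SAP 3.3. The signed-off plan therefore carries one SVD power figure, and that figure describes a cohort that the next subsection replaces. Because 4.1.2 says that pre-specified power is maintained, a reader has reason to think that the power claims of 4.1.1 still stand.

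What is at stake is how a non-significant SVD result is read. At 84.8% power, the chance of missing a true full-dose effect of 7.3 points is about 15%. Under the revised cohort it is roughly 22% to 30%, depending on the analysis population and on the effect assumed in the low-dose and no-dose women.

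The SVD population is itself left open. The exclusion of the 298 is worded for the primary outcome analysis, and the population entry in SAP 5.8 sits in the primary-outcome estimand table. SVD could therefore be analysed in 1892 or in 2190 women.

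**Working it through.** **Inputs.** From SAP 4.1.1: 866 per arm, ICC 0.05 in the intervention arm only, mean circle size 8 with Poisson variation, 10% drop-out, 69% against 77% for the primary outcome, and 84.8% power for 7.3 points in SVD. From SAP 5.5: "all p-values will be two-sided". From SAP 4.1.2: the cohort counts and the halved effect in 532 women.

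**Step 1: the plan's own figures.** The design effect in the intervention arm is 1 + 8 × 0.05 = 1.40 (with Poisson variation, the term that replaces m − 1 equals 8). For the primary outcome, a normal approximation with pooled variance under the null has:
- pooled proportion (0.69 + 0.77/1.4) / (1 + 1/1.4) = 0.723
- null term √(0.723 × 0.277 × 2.4) = 0.693
- alternative term √(0.69 × 0.31 + 1.4 × 0.77 × 0.23) = 0.680
- n = (1.960 × 0.693 + 1.282 × 0.680)² / 0.08² ≈ 777 per arm, and 777/0.9 ≈ 864, against the stated 866.

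The primary calculation is therefore reproduced. The 84.8% for SVD cannot be reproduced independently, because no control rate is given. It is taken as correct for 1732 women.

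**Step 2: signal implied by 84.8%.** z = 1.960 + 1.028 = 2.988 at N = 1732 with the full 7.3 points. Scaling this value needs no control rate, provided that ICC, drop-out and outcome variance stay about the same.

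**Step 3: revised cohort.** Women with the full effect: 794 + 566 = 1360. The halved group counts as 0.5 × 532 = 266. Together these are 1626 full-effect equivalents. The total is 2190, or 2190 − 298 = 1892 without the low-dose and no-dose women. The slightly different counts in SAP 8.3 (795 and 531) do not alter the results.

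**Step 4: power.** With f = full-effect equivalents / N, the new z is 2.988 × f × √(N/1732), and power is Φ(z − 1.960).

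| SVD population and effect in the 298 | N | f | Mean difference (points) | z | Power |
|---|---|---|---|---|---|
| Cohort of 4.1.1, full effect | 1732 | 1.000 | 7.30 | 2.988 | 84.8% |
| 298 excluded | 1892 | 1626/1892 = 0.859 | 6.27 | 2.684 | 76.5% |
| All; none in the 298 | 2190 | 1626/2190 = 0.742 | 5.42 | 2.495 | 70.4% |
| All; half in the 176, none in the 122 | 2190 | (1626 + 88)/2190 = 0.783 | 5.71 | 2.630 | 74.8% |
| All; half in all 298 | 2190 | (1626 + 149)/2190 = 0.811 | 5.92 | 2.723 | 77.7% |

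A direct two-proportion calculation, at control rates that return 84.8% for 1732 women, agrees: about 76% for 1892 and 69–70% for 2190 with no effect in the 298.

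**Step 5: does n = 160 maintain power?** The same factor applies to any outcome. For the primary outcome, z = 1.960 + 1.282 = 3.242 at 90%. In 1892 women it becomes 3.242 × 0.859 × √(1892/1732) = 2.912, so power is about 83%. To hold the original signal with 532 half-effect women, N must satisfy (N − 266)²/N = 1732. This gives about 2233 analysed women, or about 500 above 1732 rather than 160. Optimal weighting of the two effect groups would use √((1360 + 0.25 × 532)/1732) = 0.928 as the factor. It gives about 79% for SVD and 85% for the primary outcome, so it does not restore either figure. The primary model in SAP 5.9 fits one common effect without such weighting.

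**The case against.** The strongest reply is that nothing in 4.1.1 is false. It is headed pre-covid, its sentences are tied to 1732 women, and 4.1.2 openly says that the calculation was revised. This stands: a reader might infer a slip of arithmetic, and there is none. What remains is that the figure was not updated, next to a claim of maintained power that the plan's own assumption does not bear out.

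Second, the halving is written within the recalculation for the primary outcome, and not for SVD. This also stands, so carrying it over is an assumption. It is a natural one, because the stated reason for the halving is reduced dose.

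Third, a reader might infer that the plan's own dose assumptions put SVD power at 70%. They do not. The SAP gives no effect for the 298 women, and no effect at all in them is this review's lower bound. With half the effect in the 176 low and very low dose women, power is about 75%.

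Fourth, 76% for SVD implies that 160 women were too few for the primary outcome as well. That is so, but it does not defend the plan, because Step 5 confirms it.

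A reader might also infer that the SVD control rate was borrowed from the 69% used for healthy baby, since about 70% with 10% drop-out returns the 84.8%. The document does not support this: about 65% without drop-out returns it equally well.

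Finally, SVD is secondary and the SAP already plans 95% confidence intervals for it. That limits the consequence.

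**Conclusion.** The point holds as one of an outdated and unsupported power statement. The 84.8% and the conclusion drawn from it apply to 1732 women with the full effect, and the final design does not deliver them. With the halved effect in 532 women carried over to SVD, power is about 76% if the 298 are excluded. If all 2190 are analysed, it is about 70%, 75% or 78%, as the effect in the 298 is taken as none, as half in the 176 only, or as half in all. None of these cases reaches 84.8%.

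The results rest on the 84.8% being right for 1732 women, on unchanged ICC and drop-out, on the halving applying to SVD, on a single averaged effect and, for 2190 women, on effects in the 298 that the SAP does not state. The statement that 160 women maintain pre-specified power fails on the same scaling, with the primary outcome at about 83%. Severity is minor to moderate: no analysis or decision rule depends on the SVD figure, but the reading of a null SVD result does.

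**What to change.** In SAP 4.1.2:

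1. State whether SVD is analysed in the 1892 women or in all 2190.
2. Replace the 84.8% and the sufficiency conclusion with the power for that population and the dose assumptions behind it: about 76% for 1892, or 70–78% for 2190 with the effect assumed in the 298 written out. Give the SVD control rate used, and note in 4.1.1 that its SVD statement is superseded.
3. Correct the statement that 160 women maintain pre-specified power, giving about 83% for the primary outcome under the halving with simple averaging, or show the calculation that supports 160.
4. Say that a non-significant SVD result will be interpreted from its confidence interval.

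The cost is one recalculation and a few sentences. The stated power becomes less favourable; data, models and recruitment are unchanged.

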4.1.2 Sample size calculation (recruitment unpaused)

With the approval of the TSC an extension to allow the recruitment of another n=566 women to the study in addition to the sample size above has been made after the trial was paused. This results in a final total sample size targe of n=2190. The reasons for proposing this sample size are described in the following.

The trial has been paused to recruitment because of the Covid-19 pandemic. In person pregnancy circles were stopped and women were returned to one-to-one care. At this point:

- 794 women were recruited prior to the pandemic.
- 532 women recruited prior to the onset of the pandemic had not quite completed the intervention period but had the chance to receive a high or moderate dose of the intervention.
- 176 women recruited prior to the onset of the pandemic only had the opportunity to receive a low/very low dose of the intervention.
- Finally, another 122 women were recruited and had their pregnancy during a period when no intervention delivery was possible.

At this moment, the recruitment of 106 additional women would have been needed to reach the pre-specified sample size of 1732. But since some women only received low/very low or no dose of the intervention, we revised the sample size calculation to address the reduced chance of observing the pre-hypothesised effect size in the cohort already recruited.

With the approval of the TSC the decision was made to exclude all women who during the pandemic were not able to receive the intervention or were only able to receive a low/ very low dose during the pandemic from the primary outcome analysis (NB data from these women will still be analysed, just not as part of the primary outcome analysis). Additional women are recruited to replace these n=298 women. For the participant cohort who could have received a moderate or high dose of the intervention during the pandemic the assumption was made the treatment effect was halved which

requires an inflation of the sample size by n=160 to maintain pre-specified power. Thus together with 108 participants who had yet to be recruited the total post-pandemic recruitment target is n=108+160+298=566.

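### Adding 160 women does not keep 90% power: with the effect halved in 532 women, the SAP's own inputs give about 83%

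*SAP*

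**What the plan says.** Section 4.1.1 gives the original design. It targets an 8-point difference in the proportion of healthy babies, and "with 90% power and a 5% significance level, we would require at least 866 women per arm", 1732 in total. "This calculation also assumed an outcome proportion of 69% in the control arm". It also "accounts for clustering within the intervention arm with an intra-cluster correlation (ICC) of 0.05" in that arm, takes a mean circle size of 8 with Poisson variation, and allows 10% drop-out in both arms. Section 5.5 adds that "all p-values will be two-sided".

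Section 4.1.2 revises the target after the pandemic pause. Of the women already recruited, 794 came before the pandemic, and "532 women recruited prior to the onset of the pandemic had not quite completed the intervention period" but could have received a high or moderate dose. A further 176 (low or very low dose) and 122 (no intervention), 298 together, are excluded from the primary outcome analysis and replaced. For the 532, the effect is assumed to be halved, which "requires an inflation of the sample size by n=160 to maintain pre-specified power". New recruitment is 108 + 160 + 298 = 566, for a total of 2190. No formula for the 160 is given.

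**The concern.** The 532 women make up more than a quarter of the primary analysis set. Halving the effect in so large a share lowers the average effect by about 14%. Since the required sample size varies with the inverse square of the effect, a 9% increase (160 on 1732) looks far too small to compensate.

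The sentence is the justification for the redesigned sample size. If it is carried into the report, readers will believe that the trial kept a 10% type II error on its own assumptions when it did not. That matters most if the primary result is null.

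**Working it through.** **Inputs (SAP 4.1.1, 4.1.2, 5.5).** Control proportion 0.69; difference 0.08; two-sided 5%; ICC 0.05 in the intervention arm only; mean circle size 8 with Poisson variation, so squared coefficient of variation 1/8; drop-out 10%; 1:1 allocation; effect halved in 532 women.

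**Design effect, intervention arm.** 1 + (8 × (1 + 1/8) − 1) × 0.05 = 1.40.

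**Power formula.** Power = Φ(d/SE − 1.96), where SE = √{[p₀(1 − p₀) + 1.40 × p₁(1 − p₁)]/n} and n is the number per arm after drop-out.

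**Step 1: reproduce the original design.**
- n = 866 × 0.9 = 779.4; p₀ = 0.69; p₁ = 0.77.
- SE = √[(0.2139 + 1.40 × 0.1771)/779.4] = 0.02434.
- d/SE = 0.08/0.02434 = 3.286. Power = Φ(1.326) = 90.8%.
- With a pooled variance under the null, power is 90.4%.
- The total needed for 90% is 1685 (unpooled) or 1710 (pooled), within 3% of the stated 1732.

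The method therefore agrees with section 4.1.1.

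**Step 2: the primary analysis set.** 2190 − 298 = 1892, and also 794 + 532 + 566 = 1892. Full effect: 794 + 566 = 1360. Half effect: 532.

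**Step 3: the average effect.** (1360 × 8 + 532 × 4)/1892 = 6.88 points. The primary model in section 5.9 fits a single treatment effect with no term for dose cohort, so this average is what the test detects.

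**Step 4: power of the revised design.**
- n = 1892/2 × 0.9 = 851.4; p₁ = 0.69 + 0.0688 = 0.7588.
- SE = √[(0.2139 + 1.40 × 0.1830)/851.4] = 0.0235.
- d/SE = 0.06875/0.0235 = 2.926. Power = Φ(0.966) = 83.3%.

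**Step 5: variants.**

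| Variant | Power at 1892 |
|---|---|
| Unpooled variance | 83.3% |
| Pooled variance | 82.8% |
| Scaling from 1732 = exactly 90% | 82.9% |
| Design effect tuned so that 1732 gives exactly 90% | 82.3% |
| Effect halved on the log-odds scale (unpooled) | 83.9% |
| No drop-out | 86.5% to 86.9% |
| Optimal weighting of the two cohorts (not planned) | 85% to 86% |

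Using 531 women, as in appendix 8.3, makes no material difference.

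**Step 6: the inflation that would keep 90%.** Solve for N with average effect 0.08 × (1 − 266/N), where 266 is half of 532. The unpooled formula gives 2211 and the pooled formula 2232; the versions tuned to 1732 = 90% give up to 2260. The inflation is 2211 − 1732 = 479 up to about 530. With no inflation (1732 women) power would be 78% to 79%, so the 160 recovers only part of the loss.

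**Step 7: what 160 would cover.** By simple scaling, 1892 women keep 90% power if the effect in the 532 falls by (1 − √(1732/1892)) × 1892/532 = 15%, not 50%. Equivalently, the number of women with a halved effect would have to be 2 × 1892 × (1 − √(1732/1892)) = 164. The unpooled formula, which starts from slightly more than 90%, allows about 201.

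**The case against.** **This is a planning paragraph.** The error does not touch the analysis population, the estimand, the model or alpha, and there are no formal stopping rules. A null result will be read mainly from the odds ratio and risk difference with their confidence intervals, which do not depend on planned power. This is true, and it limits the consequences: nothing in the results becomes biased or invalid. But the SAP makes a definite power claim, the redesigned target rests on it, and it is wrong on the SAP's own inputs.

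**A single power figure is too definite.** It assumes the full effect in all 566 later recruits, halving on the risk-difference scale, and 10% drop-out also among women already recruited; it leaves out the adjustment for site and English level. The derivation of 160 may be recorded in the protocol, which was not available here. These are fair reasons to state the assumptions beside the figure. They do not close the gap: the variants run from about 82% to 87%. A formula held elsewhere could explain where 160 came from, but could not reconcile it with a halved effect in 532 women and 90% power.

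**Other readings.** Halving the effect only in the moderate-dose group (154 intervention women in appendix 8.3, roughly 308 with controls) gives about 88%, but section 4.1.2 names moderate and high dose together. Counting only the 271 intervention women as affected would need about 262 extra. Neither yields 160.

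**Conclusion.** The concern holds. On the inputs in sections 4.1.1 and 4.1.2, the 1892 women in the primary analysis give about 83% power (82.3% to 83.9% with 10% drop-out), not 90%. The type II error is about 17% instead of 10%, and the inflation needed was about three times the one stated.

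This rests on the SAP's own assumptions: half effect in 532 women, full effect in the other 1360, 69% in the control arm, a design effect of 1.40 in the intervention arm and 10% drop-out. It is a planning figure; actual power will depend on the numbers achieved and the true ICC.

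**What to change.** In section 4.1.2, replace the statement that 160 extra women maintain the pre-specified power. Suggested text: *With 1892 women in the primary analysis (1360 assumed to have the full effect, 532 half the effect) the average assumed effect is 6.9 percentage points and power is about 83%, using the control proportion, ICC, circle size and drop-out of section 4.1.1.* If the sponsor has a derivation of the 160, its formula and assumptions should be set out there too. Use the corrected power wherever the trial report describes the sample size.

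The cost is a change of wording and a less favourable stated power. It needs no unblinded data and no change to the analysis, and no extra recruitment is proposed.

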4.2 Randomisation procedure

Women will be randomised to receive current standard mid-wife led antenatal care (control) or entered in the pregnancy circles groups (intervention) with a 1:1 allocation ratio. If recruited in person, each woman will be told her allocation status face-to-face straight away. Each pregnancy circle will consist of 8-12 pregnant women who have estimated delivery dates within the same approximate one-month period. Women will be randomised using randomly permuted blocks of 4, 6 or 8 and randomisation will be stratified by the location (site) of the Pregnancy Circle and on a woman's ability to speak English a) well/very well or b) not well/not at all.

4.3 Blinding

Participants and maternity staff will be unblinded to allocations, along with the researchers conducting the process evaluation observations and interviews. However, data informatics staff supplying outcome information from electronic records and researchers accessing paper records for outcome information will be blinded to allocation. Furthermore, all individuals contributing to the analysis plan and those conducting the analysis at the PCTU will be blinded to intervention allocation until the formal SAP has been signed off and the database locked for analysis.

5. Analysis methods

5.1 Data cleaning process

Blinded data cleaning has been an ongoing process for the routine maternity data which includes the primary outcome amongst other data related to birth. These data were sent in excel files by sites and data cleaning included range, logical and consistency checks and identifying unreported Serious Adverse Events as defined in the protocol. The process of creating queries has been handled with Stata. Data cleaning reports were then sent to the trial manager to communicate with sites for data correction to ensure the quality of the data before it is locked for the final analysis. A summary of issues identified prior to sign off of the SAP is provided in Appendix Table 17

Data collected on REDCap are self-reported questionnaires that patients have completed throughout the trial. As it was not possible to get back to patients to eventually amend their responses, limited data cleaning is possible on these data. Consistency checks described below will be made and summarised in a table in an appendix to the statistical analysis report.

- 1) Consistency of English level between Randomisation data and baseline questionnaire.
- 2) Check that all randomised participants who have not withdrawn before randomisation have correctly been assigned to a pregnancy circle.
- 3) Consistency check: estimated delivery date should be equal to confirmed delivery date more or less 4 months.

- 4) If AE/SAE has a start date then there should be a description.
- 5) End date of AE/SAE must be equal or greater than start date.

